9.4 RECORD RETENTION AND ARCHIVING

Data and all appropriate documentation will be stored for a minimum of 5 years after the completion of the study, including the follow-up period.

10.2 MONITORING AT TRIAL COORDINATING CENTRE

Each GP practice will update the online CRF (VIDAL app) with details of new participants as they are enrolled into the trial (see section 5). The GP practice will also send copies of each participant's signed informed consent to the Trial Coordinating Centre. The Trial Coordinating Centre (and automated VIDAL app) will then confirm participant eligibility by (i) checking that the signed informed consent is satisfactorily completed, (ii) checking that the corrected serum calcium result has been entered on the website and is no higher than 2.65 mmol/L, and (iii) checking that the online lifestyle questions have been satisfactorily completed for each participant. Participants will then be contacted by the Trial Coordinating Centre to check that they are still willing to participate in the trial before being randomised as per section 5.1.5 of this protocol.

The online CRF (VIDAL app) will send weekly reminders to each GP practice, listing all randomised participants with scheduled or overdue quarterly follow-ups. The Trial Coordinating Centre will monitor adverse events, compliance and change of address online and telephone practices to give appropriate reminders. Copies of all postal communications and paper versions of baseline visit data from 10% of participants to each

GP practice will also be posted to the Trial Coordinating Centre for quality control purposes.

Following randomisation, the Trial Coordinating Centre staff will check, log on the VIDAL app, and file all returns received by post from participants confirming that they have received their correct medication pack (12 bottles labelled by month) and recording the date when their first dose was taken. Non-responders will be telephoned within 2 weeks to check receipt of medication. This process will be repeated when the treatment pack for the second year is sent. Following the second (2-year) visit to the GP practice, the Trial Coordinating Centre will monitor the VIDAL app to confirm that the repeat blood test was taken and the lifestyle questions were satisfactorily completed. Participating GP practices will also check the used treatment packs and unused study oil (brought in to the practice by each participant at their final visit). The practice will cross-check the study oil dose dates supplied on the front of the treatment packs against the dates provided in the 3-monthly follow-ups for consistency, querying any discrepancies with the patient. In addition, practices will also cross-check unused doses of study oil brought back by each participant against the quarterly follow-up compliance information.

All tracking and CRF data will be entered onto the VIDAL app as described in section 5. Data quality will be audited according to GCP guidelines, and an audit trail will be maintained of any change or correction to the electronic database. Data will be generated, recorded and reported in compliance with the protocol and with Good Clinical Practice.

10.3 MONITORING AT LOCAL SITE

This is a low risk study with minimal source data to verify. Most data obtained in the GP practices will be recorded directly onto the online CRF (VIDAL app), including email replies to 3-monthly follow-ups, which will be routed directly to the VIDAL App. Additional source data documents that will be retained at the GP practice will be signed consent, paper versions of the baseline visit data and communications from participants (postal, and copies of any e-mails), and from the GP practice to the Trial Coordinating Centre. Copies of all signed consent forms and the paper versions of baseline visit data and postal and e-mail communications from a random sample of participants, will be forwarded to the Trial Coordinating Centre for central monitoring purposes. The distribution of blood calcium results and SAEs will also be monitored at each site for unusual patterns. Following the initial training of practice staff from each site to establish and confirm procedures, monitoring at local sites will only take place if issues are identified through the central monitoring process.

11. REGULATORY ISSUES

11.1 CLINICAL TRIAL AUTHORISATION (CTA)

The trial will be conducted in accordance with the Medicines for Human Use (Clinical Trials) Regulations and subsequent amendments. An application for Clinical Trials Authorisation from the MHRA is approved (reference: 17072/0006/001-0001).

11.2 ETHICS APPROVAL

The Trial Coordinating Centre has obtained approval from the London - Chelsea Research Ethics Committee (REC reference: 11/LO/1989). The study must also be submitted for Site Specific Assessment (SSA) at each participating Primary Care Trust (PCT). The study will be conducted in accordance with the recommendations for physicians involved

in research on human subjects adopted by the 18th World Medical Assembly, Helsinki 1964 and later revisions.

11.3 CONSENT

Consent to enter the study will be sought by the practice nurse from each participant only after an information leaflet has been sent and a minimum of 24 hours allowed for consideration, and a full explanation has been given at the visit to the GP practice. Signed participant consent will then be obtained, but participants will not be randomised until a subsequent telephone call from the Trial Coordinating Centre to confirm that they are still happy to participate. All participants are free to withdraw at any time from the protocol treatment without giving reasons and without prejudicing further treatment. In these cases the participants remain within the study for the purposes of follow-up and data analysis, unless permission for this is specifically withdrawn.

11.4 CONFIDENTIALITY

Participants' identification data will be required for the registration process, for despatching the drugs, for follow-up, and for flagging purposes. The Trial Coordinating Centre will preserve the confidentiality of participants taking part in the study and is registered under the Data Protection Act.

11.5 INDEMNITY

London School of Hygiene & Tropical Medicine holds Public Liability ("negligent harm") and Clinical Trial ("non-negligent harm") insurance policies which apply to this trial.

11.6 SPONSOR

London School of Hygiene & Tropical Medicine will act as the sponsor for this study. Delegated responsibilities will be assigned locally.

11.7 FUNDING

The NIHR Health Technology Assessment programme is funding this study.

11.8 AUDITS AND INSPECTIONS

The study may be subject to audit by the London School of Hygiene & Tropical Medicine under their remit as sponsor, the Trial Coordinating Centre and other regulatory bodies to ensure adherence to the protocol, GCP and all applicable regulatory requirements.

11.9 LEAD PRIMARY CARE TRUST (PCT) AND COMPREHENSIVE RESEARCH NETWORK (CLRN)

The lead Primary Care Trust (PCT) for this study is Camden PCT and the lead Comprehensive Local Research Network (CLRN) is the Central and East London CLRN.

12. TRIAL MANAGEMENT

The investigators and Trial Coordinator will constitute the Trial Management Group (TMG), which will be responsible for overseeing the progress of the trial. The day-to-day management of the trial will be co-ordinated through the Trial Coordinating Centre at the London School of Hygiene & Tropical Medicine. The Cancer Prevention Trials Unit at

Queen Mary University of London will provide a web-based system (the VIDAL app) to capture data electronically, incorporating a trial database and a system to carry out randomisations (see section 5.1.1). The specifications of the system will be defined by the Trial Coordinating Centre at the London School of Hygiene and Tropical Medicine and a service level agreement will be signed between the London School of Hygiene and Tropical Medicine and Queen Mary University of London to that effect.

12.1 DATA MONITORING COMMITTEE

a) A data monitoring committee (DMC), which will include an independent statistician, will be convened for the trial by the chairman ([name], Oxford University) and will meet at least annually. The chairman of the DMC will keep a record of DMC communications and activities. The central responsibility of this DMC will be to make recommendations to the Sponsor and the Trial Management Group on the conduct of this trial, based on results of the monitoring procedures described above. Such recommendations could include continuing or terminating the trial, or modifying its protocol. Any such modifications should not violate the concepts behind the original study protocol. If changes in the study conduct are recommended by this DMC, sufficient information should be provided to allow the Sponsor and Trial Management Group to decide whether and how to implement them.

12.1.1 Maintenance of trial treatment randomisation codes and procedures for breaking codes

Nova Laboratories Ltd will provide a list of all treatment packs giving the pack codes and contents (whether vitamin D or placebo) to independent trialists at The Cancer Prevention Trials Unit at Queen Mary University of London, who will also have web access to a list of all randomised participants and their allocated treatments (see section 5.2). Staff at The Cancer Prevention Trials Unit at Queen Mary University of London may unblind a participant's allocation at the request of a GP according to the VIDAL Trial Standard Operating Procedure for emergency code breaking.

12.1.2 Monitoring procedures

The DMC will review accumulating data in an unblinded fashion in order to monitor safety, efficacy and quality of study conduct.

(a) Safety monitoring

At least annually, the Trial Management Group will collate and clean data detailing all known serious adverse events to date in trial participants, together with an updated HES download of all hospital admissions, and send these data to an independent statistician. The statistician will then conduct an analysis to compare the incidence of SAEs between intervention and control groups for review by the DMC, and the DMC will inform the Trial Management Group whether new findings for the subjects of the trial have changed the benefit / risk ratio of conducting the trial.

(b) Monitoring quality of study conduct

If the DMC observes problems with the study conduct (e.g. with respect to protocol adherence, recruitment or participant withdrawal), it should consider making recommendations to the investigators and the sponsor to improve the quality of the study.

12.1.3 Declaration of possible conflicts of interest of DMC members

The members of the DMC will have no involvements that might raise the question of bias in their reports to the sponsor or investigators in this study. Specifically, they will have no financial interest in the outcome of this study, and they will not be authors on publications arising from this study.

12.1.4 Frequency and format of DMC meetings

It is anticipated that the DMC will be able to conduct all of its business by email and telephone call, rendering a physical meeting between members, investigators and representatives of the sponsor unnecessary. The DMC will review safety analyses at least annually.

12.1.5 Communication Procedures

The DMC will communicate results of safety and efficacy analyses by email to the Trial Management Group. When a GP requests that a participant be unblinded, the Cancer Prevention Trials Unit at Queen Mary University of London will communicate directly with that GP by email or by telephone.

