5.2 UNBLINDING

A list of all randomised participants specifying name, sex, date of birth, practice, allocated treatment and corresponding pack code(s), will be accessible from the online CRF (VIDAL app) by independent trialists at The Cancer Prevention Trials Unit at Queen Mary University of London, to enable them to break the code if clinically necessary, but will not be accessible by any VIDAL Trial personnel. Specified staff at The Cancer Prevention Trials Unit at Queen Mary University of London will also be given a copy of the file provided by Nova Laboratories specifying the pack codes and contents (whether vitamin D or placebo) of all treatment packs. As this is a study of a micro-nutrient at a dose below the tolerable upper intake limit, 24-hour unblinding is not necessary.

A GP or the sponsor may request an emergency code break in the following circumstances:

- a) In case of a suspected serious adverse reaction (SAR or SUSAR) where knowledge of participant allocation may influence clinical management of a study participant.
- b) In any other circumstance in which the GP or clinical CI considers that an emergency code-break is indicated.

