9.3.3 Interim reports

A Data Monitoring Committee will be convened (see section 12.1). Interim safety and recruitment analyses will be conducted annually for this feasibility study. The Trial Management Group will collate and clean data detailing all known serious adverse events to date in trial participants. The trial statistician will then conduct an analysis to compare the incidence of SAEs between intervention and control groups, for review by the DMC. If there is a significant difference (p<0.01) in the incidence of fatal or life threatening adverse events an emergency meeting of the DMC will be convened and the Sponsor and Ethics Committee will be consulted to decide whether the trial should be stopped.

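### Sections 9.3.3 and 12.1.2 name different statisticians for the same by-arm SAE analysis, and 12.1.5 lets the DMC pass more interim information to the Trial Management Group than 12.1.2 or 12.1 allows

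*Protocol*

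**What the plan says.** Two matters are each described more than once in the protocol.

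**Who runs the interim SAE comparison.** Section 9.3.3: "The trial statistician will then conduct an analysis to compare the incidence of SAEs between intervention and control groups, for review by the DMC". Section 12.1.2(a) has the Trial Management Group collate and clean the same data and "send these data to an independent statistician", who then makes the comparison for the DMC.

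**What the DMC passes on.** Section 12.1.2 says "The DMC will review accumulating data in an unblinded fashion", and then that "the DMC will inform the Trial Management Group whether new findings for the subjects of the trial have changed the benefit / risk ratio". Section 12.1 makes recommendations the DMC's central responsibility and adds that, if it recommends changes in study conduct, it should give the Sponsor and the Trial Management Group enough information to decide on them. Section 12.1.5 has no such limit: "The DMC will communicate results of safety and efficacy analyses by email to the Trial Management Group".

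Section 12 defines the Trial Management Group as the investigators and the Trial Coordinator. On blinding, section 5.2 says that the list of randomised participants with their allocations can be opened by independent trialists at the Cancer Prevention Trials Unit, "but will not be accessible by any VIDAL Trial personnel". Section 6.5.3 adds that in the double-blind practices neither participant nor investigator knows an individual's allocation.

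**The concern.** A DMC sees unblinded comparisons so that the trial team need not. Here one section may place the unblinded analysis inside the team, and another sends its results to the team.

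What is at stake is the safety evidence from the double-blind practices. Section 2.2(ii) wants unbiased adverse event data for vitamin D against placebo, and section 3.1.2(iii) restricts the SAE comparison to blinded practices, so the open-label half cannot stand in for it. The Trial Management Group prepares the SAE data (9.3.3, 12.1.2) and authorises publications (13). The Clinical Chief Investigator is told of every SAE notification (7.3.3), and the Sponsor / Clinical Chief Investigator reviews SAEs after the GP has assigned causality (7.2). Knowing which way the interim comparison points could affect queries, data cleaning and review of later events.

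**Working it through.** The point rests on no sample size, power or event count, so there is no figure to reproduce. The check is a comparison of sections.

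| Question | One section | Another section | Consistent? |
|---|---|---|---|
| Who compares SAEs by arm? | 9.3.3: trial statistician | 12.1.2(a): independent statistician | No |
| What reaches the Trial Management Group? | 12.1.2(a): whether benefit/risk has changed; 12.1: recommendations, with enough information to act on a recommended change | 12.1.5: results of the analyses, no restriction | No |
| Which interim analyses are planned? | 9.3.3: safety and recruitment | 12.1.2, 12.1.5 and 12.1.6: efficacy also mentioned | No |

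**Step 1: is it the same analysis?** In both 9.3.3 and 12.1.2(a) the Trial Management Group collates and cleans all known SAEs, a statistician compares intervention with control, and the DMC reviews the result, at annual or at-least-annual frequency. It is the same analysis, and the protocol does not say that the two titles mean one person.

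**Step 2: would the results in 12.1.5 be comparative?** The section does not say so. However, the only SAE analysis described anywhere is between groups, and the DMC reviews data unblinded. Nothing limits the e-mail to pooled figures, so the natural reading is that comparative results may be sent.

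**Step 3: does this disclose who received what?** Not directly. The lists protected by 5.2 are participant-level, and 12.1.5 speaks of results. An indirect route exists because the recipients also hold the participant-level SAE records. If a type of event has occurred once in the double-blind practices and is tabulated by arm, that participant's allocation can be read off. Section 8 itself expects too few deaths, cancers and hospital admissions for useful analysis, so sparse tables are likely.

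**Step 4: how many people and how often?** The double-blind practices hold 400 + 400 = 800 of 1,600 participants (9.1). The study lasts 3 years (1 of recruitment, 2 of treatment). Annual review implies at least two reviews before the end, at about years 1 and 2, if reviews start within the first year or so. These figures describe exposure, not bias.

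**The case against.** The case for a lesser reading is substantial.

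- **Undone blinding.** A reader might infer that 12.1.5 undoes the promised blinding. The documents do not support that. Sections 5.2 and 6.5.3 protect individual allocation, the latter only in double-blind practices, and group-level results breach neither.
- **A necessary breach of 5.2.** A reader might also infer that the trial statistician could not do the 9.3.3 analysis without breaching 5.2. That does not follow. The protocol does not say whether this person counts as VIDAL personnel or sits on the Trial Management Group, and a comparison of coded groups could be run without the list. Section 9.3.3 also refers to section 12.1, so loose naming of one person is plausible.
- **Causality.** It would be wrong to say that the Trial Management Group assigns causality. The GP does so first (7.2) and central review follows.
- **Data capture.** Practices record SAEs within 24 hours (7.3.3). Admissions, cancers and deaths are also found automatically through HES and the NHS Information Centre (7.3.1), which limits the scope for biased ascertainment.
- **Intended disclosure.** Section 12.1 plainly intends some disclosure when a change is recommended.
- **Main analyses.** These compare recruitment and compliance between designs (9.3.1), and no path leads to them from an interim vitamin D against placebo SAE result.

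All of this stands and sets the limits of the point. It does not remove the two mismatches. Loose naming still leaves staff unsure who may hold unblinded data, and the narrower message in 12.1.2 does not cancel the open-ended one in 12.1.5. Disclosure tied to a recommended change is also not the same as routine release of results.

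**Conclusion.** The point holds as an internal inconsistency with a practical consequence. The protocol names two different statisticians for one by-arm SAE analysis, and 12.1.5 allows more to reach the Trial Management Group than 12.1.2 or 12.1. Applied literally, it gives the investigators interim comparative results while follow-up continues. That weakens the separation between DMC and trial team and puts at risk the blinding of secondary safety outcomes in the double-blind practices, especially when events are few.

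The conclusion rests on two assumptions: that the results in 12.1.5 are by arm, as the only SAE analysis described is, and that the investigators in section 12 include those who handle or review SAE data. The textual mismatch is certain. The amount of bias cannot be estimated from the protocol and may be small. The change should be made because the exposure is easily avoided, not because harm to the main results has been shown.

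**What to change.** 1. In 9.3.3, replace the trial statistician with the independent statistician of 12.1.2, and state in both places that the Cancer Prevention Trials Unit supplies the allocation codes to that person directly.
2. In 12.1.5, align the text with 12.1.2 and 12.1: the DMC sends the Trial Management Group its benefit/risk statement and its recommendation. Comparative results are released only as far as needed when the DMC recommends a change or stopping the trial. The emergency consultation with the Sponsor and Ethics Committee in 9.3.3 can stay as it is.
3. In 12.1.5, delete the reference to efficacy analyses or reconcile it with 9.3.3, which plans only interim safety and recruitment analyses. Treat the matching references in 12.1.2 and 12.1.6 the same way.

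The cost is a few sentences. The independent statistician and the code-holding unit are already in the protocol, so no new role, data or analysis is needed.

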12.1.6 Documentation of the DMC activities

The DMC will keep a record of any safety and efficacy analyses performed, and the Cancer Prevention Trials Unit at Queen Mary University of London will keep a record of the circumstances in which it unblinded any participant's allocation.

13. PUBLICATION POLICY

All publications and presentations relating to the study will be authorised by the Trial Management Group. The first publication of the trial results will be in the name of the Trial Management Group, if this does not conflict with the journal's policy. Authorship of parallel studies initiated outside of the Trial Management Group will be according to the individuals involved in the project but must acknowledge the contribution of the Trial Management Group and the Trial Coordinating Centre.

APPENDIX 1: SUMMARY OF INVESTIGATIONS, TREATMENT AND ASSESSMENTS

[figure not shown]
| | Visit 1 | Telephone Call | IMP sent | Post or email | Post or email | Post or email | Post or email | IMP sent | Post or email | Post or email | Post or email | Post or email | Visit 2 |
|--|----------|-------------------|--|---------------|---------------|---------------|---------------|----------|---------------|---------------|---------------|---------------|----------|
| | -4 weeks | -1 week | 0 Weeks | Month 3 | Month 6 | Month 9 | Month 12 | Month 12 | Month 15 | Month 18 | Month 21 | Month 24 | Month 24 |
| Sign consent forms | x | | | | | | | | | | | | |
| Eligibility checked | Х | | | | | | | | | | | | |
| Give personal/medical details | Х | | | | | | | | | | | | х |
| Complete online CRF | Х | | | | | | | | | | | | х |
| Blood pressure, waist circumference, height and weight measured | х | | | | | | | | | | | | х |
| Give blood sample | Х | | | | | | | | | | | | х |
| Confirm eligibility and willingness to be randomised | | х | | | | | | | | | | | |
| Randomisation, IMP sent, (unless open control), medication receipt confirmed | | | х | | | | | х | | | | | |
| Monthly reminder to take study medication | | | Automated phone call, e-mail or text every month from month 1 - 24 to remind participants to take their study medication | | | | | | | | | | |
| Take study medication | | | Study medication taken every month from when it is received at week 0 and month 12 (24 times in total) | | | | | | | | | | |
| Confirm medication taken | | | x | | | | | | | | | | |

VIDAL Trial Protocol Page 43 of 45 Version 3, 25.07.2012

